6.5.4. Vital Signs

Vital signs data includes weight, pulse, systolic blood pressure, and diastolic blood pressure. Measurements were only to be provided once per timepoint. If multiple assessments are provided per timepoint, the maximum value will be used for reporting.

The number and percent of patients in each of the following minimum and maximum blood pressure, body weight, and pulse categories will be presented:

- Increase in Systolic Blood Pressure ≥ 40 mmHg;
- Decrease in Systolic Blood Pressure ≥ 40 mmHg;

- Increase in Diastolic Blood Pressure ≥ 20 mmHg;
- Decrease in Diastolic Blood Pressure ≥ 20 mmHg;
- Increase in Diastolic Blood Pressure ≥ 60 mmHg;
- Decrease in Body Weight $\geq 10\%$;
- Increase in Body Weight between 10% and 20%;
- Increase in Body Weight (increase) $\geq 20\%$;
- Maximum Pulse Rate > 120 bpm;
- Minimum Pulse Rate < 50 bpm;
- Maximum increase in pulse rate ≥ 30 bpm;
- Maximum decrease in pulse rate ≥ 30 bpm.

All assessments, including unscheduled assessments will be considered. A patient can be included in multiple categories if different criteria are met at different timepoints.

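### SAP 6.5.4 keeps the highest of several same-timepoint vital signs whatever the direction, so the downward categories can be misclassified where duplicate readings exist

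*SAP*

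**What the plan says.** SAP 6.5.4 covers four parameters: "Vital signs data includes weight, pulse, systolic blood pressure, and diastolic blood pressure". It treats duplicates as unplanned: "Measurements were only to be provided once per timepoint". If they occur anyway, "If multiple assessments are provided per timepoint, the maximum value will be used for reporting". No parameter and no direction of change is exempt.

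The section then announces its tables: "The number and percent of patients in each of the following minimum and maximum blood pressure, body weight, and pulse categories will be presented". Five of the listed categories look downward:

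- "Decrease in Systolic Blood Pressure", threshold 40 mmHg
- "Decrease in Diastolic Blood Pressure", threshold 20 mmHg
- "Decrease in Body Weight", threshold 10%
- lowest pulse under 50 bpm
- largest pulse fall of at least 30 bpm

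After the list comes "All assessments, including unscheduled assessments will be considered". SAP 5.2.13 likewise brings unscheduled assessments into baseline and worst-case on-treatment derivations for safety. SAP 3.4 takes the last assessment before first dose as baseline.

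**The concern.** A count of patients with a low value needs the low value. A rule that keeps only the highest reading at a timepoint suits the upward categories and works against the downward ones. Where it applies, a patient who met a downward category on one reading can be left out of the table.

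Low pulse has some relevance here. Protocol 5.5.2 describes PR prolongation with lorlatinib, and exclusion criterion 11 defines bradycardia as under 50 bpm, the same cut-off as this table. SAP 6.5.5 has categories for QTc, PR and QRS but none for low heart rate. The vital-signs table is therefore the only threshold count of low pulse in the SAP text available. With planned cohorts of 66 and 34, one misclassified patient moves a percentage by 1/66 = 1.5 points or 1/34 = 2.9 points.

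**Working it through.** The plan gives no figure to reproduce on this point. The check applies the SAP's rule to its own thresholds. All readings below are assumed for illustration.

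**1. Duplicate post-baseline readings, single baseline value**

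| Category | Baseline | Two readings | Using the lower | Using the maximum |
|---|---|---|---|---|
| Systolic fall ≥40 mmHg | 150 | 108, 116 | 150 − 108 = 42, counted | 150 − 116 = 34, missed |
| Diastolic fall ≥20 mmHg | 85 | 64, 70 | 85 − 64 = 21, counted | 85 − 70 = 15, missed |
| Weight loss ≥10% | 60.0 kg | 53.8, 54.6 | 6.2/60.0 = 10.3%, counted | 5.4/60.0 = 9.0%, missed |
| Lowest pulse <50 bpm | not used | 48, 54 | 48, counted | 54, missed |
| Pulse fall ≥30 bpm | 85 | 54, 60 | 85 − 54 = 31, counted | 85 − 60 = 25, missed |

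The loss is not automatic. With 44 and 48 bpm the maximum is 48, and the patient is still counted as under 50.

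**2. How strongly the rule leans, given two readings**

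Let p be the chance that one reading meets the threshold, with independent readings and a fixed baseline. Then P(counted by maximum) = p², and P(counted by lowest) = 1 − (1 − p)². For a true systolic fall of exactly 40 mmHg, p = 0.50, so the maximum rule gives 0.25 and the lowest reading 0.75. A simulation of 400,000 pairs with normal within-timepoint variation, its SD assumed, agrees:

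| SD (mmHg) | True fall (mmHg) | Single reading | Maximum rule | Lowest reading |
|---|---|---|---|---|
| 3 | 35 | 0.047 | 0.002 | 0.093 |
| 3 | 45 | 0.952 | 0.906 | 0.998 |
| 5 | 35 | 0.158 | 0.025 | 0.291 |
| 5 | 45 | 0.841 | 0.707 | 0.974 |
| 8 | 35 | 0.266 | 0.071 | 0.462 |
| 8 | 45 | 0.734 | 0.539 | 0.929 |

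A rise of the same size is counted under the maximum rule with the probability in the last column, so rises and falls are treated unequally.

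**3. Duplicate baseline readings**

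Take baseline systolic readings of 140 and 150 and a single later value of 108. Maximum as baseline: 150 − 108 = 42, counted. Mean: 145 − 108 = 37, not counted. Minimum: 140 − 108 = 32, not counted. Here the maximum rule adds a fall. The under-50 bpm category uses no baseline, so it cannot be overcounted in this way.

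**4. Does the text override the rule?**

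The sentence on considering all assessments, and SAP 5.2.13, bring in unscheduled assessments. Neither says what happens to two values at the same timepoint. SAP 3.4 and the maximum rule can also point to different baseline values when readings are duplicated, and the SAP does not say which prevails.

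**5. Comparison within the SAP**

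SAP 6.5.3 takes the worst grade when same-day baseline laboratory values cannot be ordered. SAP 6.5.5 averages ECG replicates and requires individual QTc values of 500 msec or more to be described when the mean hides them. Section 6.5.4 has neither a direction-aware rule nor such a safeguard.

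**The case against.** The rule is a contingency. The SAP expects one reading per timepoint, and the protocol plans no replicate vital signs, unlike the triplicate ECGs. Falls at single-reading timepoints are unaffected. The tables count patients, so someone who qualifies at any other timepoint is still included. A low value recorded as an unscheduled assessment may enter through the all-assessments sentence, and if that sentence governs the categories, nothing is lost. PR prolongation and AV block are followed by ECG, protocol 9.5.3 also summarises heart rate and RR from ECGs, and protocol 8.2.2 makes symptomatic abnormal findings adverse events.

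Most of this stands, and it limits the size of the problem. It does not remove it. The reading under which nothing is lost is possible but not stated, so two programmers could produce different counts from the same data.

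A reader might go further and infer that bradycardia and hypotension are undercounted as a matter of course, or that the loss is selective because repeats follow abnormal first values. The documents support neither. They give no rule for repeating vital signs and no duplicate rate, and for falls from baseline the error can run either way.

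**Conclusion.** As written, the rule gives the wrong answer for the downward categories whenever three things coincide: duplicate post-baseline readings at a timepoint, a retained maximum that misses the threshold, and no other qualifying timepoint. The under-50 bpm count can then only be too low. The change-from-baseline falls can be too low, or too high if duplicate baseline readings are also reduced to their maximum.

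The effect is probably small, since duplicates should be few, but the documents do not allow a count. One possible source is body weight. The schedule of activities lists it separately from vital signs, footnote 4 includes it in vital signs, and protocol 7.4.3 places it with the physical examination. Whether the CRF captures it twice is not stated. The probabilities above rest on an assumed SD, independent normal errors and exactly two readings. They show direction, not expected frequency. Only descriptive safety tables are affected; the primary endpoint is not. This is a minor correction.

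**What to change.** Replace the maximum rule in SAP 6.5.4 with a direction-specific one. For several post-baseline values at one timepoint, use the highest for the increase and maximum categories and the lowest for the decrease and minimum categories. State one direction-neutral rule for duplicate baseline readings, such as the mean or the last pre-dose value, and align it with SAP 3.4. Section 6.5.4 plans no by-visit table, so no rule is needed for one.

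The cost is one amended sentence, one added sentence and a small programming change. No new data and no change to trial conduct are needed.

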6.5.5. Electrocardiogram

Triplicate ECGs were required at each assessment. A mean score is calculated for any replicate measurements having the same nominal visit. The mean measurement is reported.

ECG summaries will include all ECG assessments from the on-treatment period. All ECG assessments will be listed, and those collected outside the on-treatment period will be flagged in the listing.

The analysis of QT data is complicated by the fact that the QT interval is highly correlated with heart rate. Because of this correlation, formulas are routinely used to obtain a corrected value, denoted QTc, which is independent of heart rate. This QTc interval is intended to represent the QT interval at a standardized heart rate.

Fridericia's correction (QTcF) will be programmatically derived using the following formula:

$$QTcF(m\ sec) = QT(m\ sec) / \sqrt[3]{RR(sec)}$$

and Bazett's correction (QTcB) will be programmatically derived using the following formula:

$$QTcB(m\ sec) = \frac{QT(m\ sec)}{\sqrt{RR(sec)}}$$

where RR represents the RR interval of the ECG, in seconds.

RR used in the above formula will be derived by $(60/\text{HR (bpm)})$ if HR is collected. Otherwise, RR will be directly used for calculation.

Additionally QTcB and QTcF (and QTcS if applicable) will be summarized by maximum on-treatment values using the following categories:

- ≤ 450 msec;
- > 450 msec but ≤ 480 msec;
- > 480 msec but ≤ 500 msec;
- > 500 msec.

Unscheduled assessments will be utilized in addition to planned assessments.

Shift tables will be provided for baseline value versus worst on-treatment value.

Additionally maximum increases from baseline (including scheduled and unscheduled assessments) will be summarized based on the following categories:

- Change > 60 msec;
- Change > 30 msec but ≤ 60 msec;
- Change ≤ 30 msec.

In the event that neither Fridericia's nor Bazett's correction adequately adjusts for heart rate, an additional correction such as a population or patient-specific baseline correction could be used and should be fully justified.

For PR and QRS maximum increases from baseline, the following categories will be applied:

- PR change $\geq 50\%$ if absolute baseline value was < 200 msec;
- PR change $\geq 25\%$ if absolute baseline value was ≥ 200 msec;
- QRS change $\geq 50\%$ if absolute baseline value was < 100 msec,
- QRS change $\geq 25\%$ if absolute baseline value was ≥ 100 msec.

If more than one ECG is measured at a nominal time post-dose (eg, triplicate ECGs within 2-4 minutes), the mean will be used to represent a single observation per patient and time post-dose. If any of the three individual ECGs results in a QTc ≥ 500 msec and the mean is not ≥ 500 msec, then that patient's data will be described in the safety section in the study report in order to place the ≥ 500 msec value in appropriate clinical context. On the other hand, such individual ≥ 500 msec value within a triplicate will not be included in the categorical analysis unless the average from that triplicate is also ≥ 500 msec. Data listings

will contain the means from a triplicate as well as the parameters from each of the three ECGs. Note that using the mean value may result in a patient having a measurement that is not represented by an actual ECG.

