10. Active and clinically significant bacterial, fungal, or viral infection including hepatitis B virus (HBV), hepatitis C virus (HCV), known human immunodeficiency virus (HIV) or acquired immunodeficiency syndrome (AIDS)-related illness.
11. Clinically significant cardiovascular disease (both arterial and venous) and non-vascular cardiac conditions, (active or within 3 months prior to enrollment, which may include, but not are limited to:
 - Arterial disease such as cerebral vascular accident/stroke (including transient ischemic attack -TIA), myocardial infarction, unstable angina;
 - Venous diseases such as cerebral venous thrombosis, symptomatic pulmonary embolism;
 - Nonvascular cardiac disease such as congestive heart failure (New York Heart Association Classification Class \geq II), second- degree or third-degree atrioventricular block (unless paced) or any AV block with PR interval >220 msec; or
 - Ongoing cardiac dysrhythmias of CTCAE Grade ≥ 2 , uncontrolled atrial fibrillation of any grade, bradycardia defined as <50 bpm (unless subject is otherwise healthy such as long-distance runners, etc.), machine-read electrocardiogram (ECG) with QTc >470 msec, or congenital long QT syndrome.
12. Subject with predisposing characteristics for acute pancreatitis according to investigator judgment, including but not limited to uncontrolled hyperglycemia, current gallstone disease, in the last month prior to enrollment.
13. History of extensive, disseminated, bilateral or presence of Grade 3 or 4 interstitial fibrosis or interstitial lung disease including a history of pneumonitis, hypersensitivity pneumonitis, interstitial pneumonia, interstitial lung disease, obliterative bronchiolitis and pulmonary fibrosis.
14. Evidence of active malignancy (other than NSCLC, non-melanoma skin cancer, or localized and presumed cured prostate cancer or any in situ cancer which does not currently require treatment) within the last 3 years prior to enrollment.
15. Concurrent use of any of the following food or drugs (consult the sponsor if in doubt whether a food or a drug falls into any of the above categories) within 12 days prior to the first dose of administration of lorlatinib:

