5.5.2. PR Interval Prolongation

Analysis of ECG data from ongoing and completed human studies with lorlatinib has identified a subset of subjects who exhibited ECG evidence of PR interval prolongation. The ECG changes appear limited to the PR interval with no impact on QRS or QT intervals. This impact on the PR interval is supported by preclinical animal studies as described in the current lorlatinib IB.

Guidance for management of PR interval prolongation is provided in [Table 3](#) below and examples of drug with potential PR interval prolongation effect can be found in [Appendix 5](#).

Table 3. PR Interval Prolongation Management

Toxicity	No symptomatic	Symptomatic
1 st -Degree Heart Block (PR interval >200 msec)	No dose hold or reduction needed. Assess concomitant medications and electrolyte imbalance that may prolong PR interval. Monitor ECG/symptoms potentially related to AV block closely	Withhold dose. Assess concomitant medications and electrolyte imbalance that may prolong PR interval. Monitor ECG/symptoms potentially related to AV block closely. If symptoms resolve, resume at same dose or at 1 reduced dose level
2 nd -Degree Heart Block	Withhold dose. Assess concomitant medications and electrolyte imbalance that may prolong PR interval. Monitor ECG/symptoms potentially related to AV block closely. If subsequent ECG does not show second degree block, resume at same dose or 1 reduced dose level	Withhold dose. Assess concomitant medications and electrolyte imbalance that may prolong PR interval. Refer for cardiac observation and monitoring. Consider pacemaker placement if symptomatic AV block persists. If symptoms and the second degree block resolve or if subjects revert to asymptomatic first degree AV block, resume at 1 reduced dose level
Complete Heart Block	Withhold dose. Assess concomitant medications and electrolyte imbalance that may prolong PR interval. Refer for cardiac observation and monitoring. Temporary pacemaker placement may be indicated for severe symptoms associated with AV block. If AV block does not resolve, placement of a permanent pacemaker may be considered. If pacemaker placed, may resume at full dose. If no pacemaker placed, resume at 1 reduced dose level only when symptoms resolve AND PR interval is less than 200 msec.	

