If a subject experiences PR interval prolongation >200 msec or second-degree or third-degree AV block, while on treatment with lorlatinib, refer to [Section 5.5.2](#).

If subject experiences a cardiac or neurologic AE (specifically syncope, dizziness, seizures, or stroke), triplicate ECGs should be obtained at time of the event. If the mean QTc is prolonged (>500 msec), or new or worsened AV block is noted, then ECGs should be re-evaluated by a qualified person at the institution for confirmation and repeated as clinically indicated. Additional triplicate ECGs may be performed as clinically indicated and relevant results reported in the CRF as 'unplanned visits' if applicable.

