9.5.3. Electrocardiograms

All ECGs obtained during the study will be evaluated for safety. The triplicate data will be averaged, and all summary statistics and data presentations will use the triplicate averaged data. Any data obtained from ECGs repeated for safety reasons after the nominal time points will not be averaged along with the preceding triplicates.

QT intervals will be corrected for heart rate (QTc) using standard correction factors (ie, Fridericia's [default correction], Bazett's, and possibly a study-specific factor, as appropriate). Data will be summarized and listed for QT, HR, RR, PR, QRS, QTc.

Descriptive statistics (n, mean, median, standard deviation, minimum, and maximum) of corrected QT interval and other ECG parameters will be used to summarize absolute values and changes from baseline on treatment. Categorical analysis will be conducted for the maximum change from baseline in corrected QT, PR, and QRS and the maximum post-baseline corrected QT interval.

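### The SAP's PR-interval categories are percentage rises that can miss new PR above 200 msec, the protocol's own first-degree block value, and no planned table counts it

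*SAP*

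**What the plan says.** **SAP 6.5.5 (Electrocardiogram).** The PR criteria open with "For PR and QRS maximum increases from baseline, the following categories will be applied". They are a change of at least 50% when baseline is below 200 msec and at least 25% when baseline is 200 msec or more. Categories for the on-treatment value itself (450, 480 and 500 msec) are given for QTc only. One sentence promises shift tables of baseline against worst on-treatment value. It stands among the QTc categories, names no parameter and defines no PR cells.

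**Protocol 9.5.3.** "Categorical analysis will be conducted for the maximum change from baseline in corrected QT, PR, and QRS and the maximum post-baseline corrected QT interval". For PR this means change only, and the SAP follows it. The same section plans descriptive statistics in which "corrected QT interval and other ECG parameters will be used to summarize absolute values and changes from baseline on treatment".

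**Protocol 5.5.2 and Table 3.** Earlier ECG data "has identified a subset of subjects who exhibited ECG evidence of PR interval prolongation". The first row of Table 3 is 1st-"Degree Heart Block (PR interval >200 msec").

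**Protocol 7.4.4.** "If a subject experiences PR interval prolongation >200 msec or second-degree or third-degree AV block, while on treatment with lorlatinib", the investigator is sent to Section 5.5.2.

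**Protocol 4.2, exclusion 11.** The entry limit is "any AV block with PR interval >220 msec", so a patient with a PR of 200 to 220 msec can enrol.

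**The concern.** ECG is a named secondary safety endpoint, and PR prolongation is an effect the protocol attributes to the drug. The protocol handles it by absolute value, with 200 msec as the line. The SAP reports it by relative change, at a point that moves with baseline and usually lies well above 200 msec.

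The PR table could therefore be empty, or nearly so, while some patients had crossed the protocol's line on treatment. A reader could take that for absence of a PR effect. The protocol also gives a model-based prediction about PR of 200 msec or more at the clinical dose (Section 1.2.3.3.3), and this study would produce no observed proportion to set beside it.

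**Working it through.** The documents state no rate or power for this point, so there is no figure of theirs to reproduce.

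**Step 1. PR value at which the SAP rule counts a patient.**
For baseline B below 200 msec the value is 1.5 × B. For B of 200 msec or more it is 1.25 × B.

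| Baseline (msec) | Counted from (msec) | Above 200 msec but not counted |
|---|---|---|
| 140 | 1.5 × 140 = 210 | above 200, below 210 |
| 150 | 1.5 × 150 = 225 | above 200, below 225 |
| 160 | 1.5 × 160 = 240 | above 200, below 240 |
| 180 | 1.5 × 180 = 270 | above 200, below 270 |
| 199 | 1.5 × 199 = 298.5 | above 200, below 298.5 |
| 200 | 1.25 × 200 = 250 | above 200, below 250 |

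**Step 2. Baselines affected.** 1.5 × B exceeds 200 when B exceeds 200 / 1.5 = 133.3 msec. So every baseline from about 133.4 to just under 200 msec has an uncounted band above 200 msec.

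**Step 3. Ordering and continuity.**
- 130 to 195 msec: 65 / 130 = 50%. Counted, although PR never exceeds 200 msec.
- 190 to 280 msec: 90 / 190 = 47%. Not counted, although PR is well past 200 msec.
- Moving baseline from 199 to 200 msec lowers the counting point from 298.5 to 250 msec, a drop of 48.5 msec for 1 msec of baseline.

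**Step 4. Share of new cases missed, under assumptions.** A new case is a baseline PR of 200 msec or less with a maximum on-treatment PR above 200 msec. The documents give no PR distribution, so these inputs are assumed:
- baseline normal, mean 145, 155 or 165 msec, SD 20 or 25, truncated to 100–220 msec;
- maximum increase normal and independent of baseline, mean 10, 20, 30 or 40 msec, SD 10, 20 or 30.

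That makes 3 × 2 × 4 × 3 = 72 scenarios, each simulated.

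| Scenario (baseline mean/SD; increase mean/SD) | New PR >200 msec | Share of these missed |
|---|---|---|
| 145/20; 40/30 (lowest share missed) | 34.0% | 66.7% |
| 155/20; 40/30 | 43.5% | 76.8% |
| 155/20; 20/20 | 17.8% | 98.6% |
| 155/20; 10/10 | 4.8% | 100.0% |

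Over all 72 scenarios the missed share runs from about 67% to 100%, and it exceeds 90% in 52 of them. The new-case column follows from the assumed increases and is not a forecast for this trial.

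**Step 5. Other outputs that might carry the count.**
- Shift table (SAP 6.5.5): no PR cells are defined, so it commits to no 200 msec split.
- Descriptive statistics (protocol 9.5.3): means, medians and extremes, but no count above a threshold.
- Listings: the values are there, but not n (%).
- Adverse events: protocol 7.4.4 asks for clinically significant ECG findings to be recorded, and 8.2.2 ties recording to symptoms, further testing, intervention or judgement. Asymptomatic first-degree block, for which Table 3 needs no dose hold, may or may not be recorded.

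**The case against.** The strongest reply is that the SAP does what protocol 9.5.3 asks: maximum change for PR, maximum value for QTc only. Table 3 guides management and does not define a reporting endpoint. This stands. The SAP is consistent with its parent section, and the mismatch is between the reporting plan and the value the protocol uses elsewhere.

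Second, little may be missed in absolute terms. Protocol 1.2.3.3.3 predicts a low probability of PR of 200 msec or more at 100 mg QD. Section 1.2.3.4 reports treatment-related Grade 1 AV block in 2 Phase 2 patients (2 / 275 = 0.7%), none in Phase 1, and none of Grade 2 or above. A reader might infer from the arithmetic that many patients will cross 200 msec unseen. The documents do not support that. They also do not support a flat statement that the criteria miss most new cases, because that rests on assumed distributions.

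Third, a reader might infer that PR is the only ECG parameter with a reported effect, since protocol 5.5.2 describes no impact on QRS or QT. Section 1.2.3.4 also reports QTc changes, with QT prolongation as a treatment-related AE in 5.4% of the 100-mg pooled group, so the point cannot rest on that.

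Fourth, there is other coverage. The SAP supplements the protocol, so its silence does not cancel the descriptive PR summaries of protocol 9.5.3. The shift-table sentence could be read to include PR. All ECGs are listed. Table 3 asks for follow-up checks even without symptoms, which may lead to an AE record. All this limits the consequence, but none of it yields a complete n (%) above 200 msec.

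**Conclusion.** The point holds as a gap in tabulation. The SAP's PR criteria can miss new PR above 200 msec for any baseline from about 133.4 to just under 200 msec, and they can count a rise that stays below 200 msec. This follows from the stated rule and needs no assumption.

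The share missed is unknown. About 67% to 100% applies only under the assumed normal distributions in the working. The number of patients concerned may be small on the protocol's own evidence. That evidence is a prediction and AE counts from another study, and no planned table here would show the observed rate.

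Data capture, patient management and the primary analysis are not affected.

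**What to change.** Keep the percentage categories in SAP 6.5.5 and add:

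1. n (%) with maximum on-treatment PR above 200 msec among patients with baseline PR of 200 msec or less, by Cohort and Total. The restriction is needed because patients with a PR of 200 to 220 msec can enter.
2. A shift table of baseline against worst on-treatment PR, 200 msec or less versus above 200 msec. Finer bands, such as a split at 220 msec, are optional.
3. A sentence restating the protocol 9.5.3 descriptive summaries of PR and its change from baseline, so that their absence from 6.5.5 is not read as removal.

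The cost is SAP wording and one or two tables from ECG data already collected. Protocol 9.5.3 allows the SAP to add this detail, and no protocol procedure changes.
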